10.3 Adverse Events

An adverse event is defined as any untoward medical occurrence in a subject. Treatment-emergent AEs (TEAE) are defined as any AE that started after dosing or prior to dosing and that worsens following exposure to the study drug. If the start date of an AE is partially or completely missing, the date will be compared as far as possible with the date of the start of administration of study drug. The AE will be assumed to be treatment-emergent if it cannot be definitively shown that the AE did not occur during the treatment-emergent period (worst case approach; see Section 6.3 for imputation algorithm).

All AEs will be coded using MedDRA version 23.1 and graded using Common Terminology Criteria for Adverse Events (CTCAE) v5.0 severity grading scale. For AEs not covered by CTCAE, the conventional definition of severity will be used as follows:

- Grade 1 (mild) AE: Minor; no specific medical intervention; marginal clinical relevance.
- Grade 2 (moderate) AE: Minimal intervention; local intervention; noninvasive intervention.
- Grade 3 (severe) AE: Significant symptoms requiring hospitalization or invasive intervention.
- Grade 4 (life-threatening or disabling) AE: Complicated by acute, life-threatening complications; need for intensive care or emergent invasive procedure.
- Grade 5: Fatal AE

For the purpose of the summaries, AEs with missing relatedness will be considered to be related to study drug and AEs with missing severity will be considered Grade 3 (severe).

Analyses of AEs will include TEAEs summarized descriptively by number of subjects with an event (n), and percentage (%), by MedDRA SOC, PT and CTCAE grade.

A subject will be counted no more than once at the SOC level and no more than once at the PT level. For summaries by SOC, PT, and CTCAE severity grade, a subject will be counted once at highest observed severity grade. Summaries by relatedness would be handled similar to the summaries by severity grade. Summaries by SOC and PT will be ordered by overall descending frequency of SOC and then, within a SOC, by overall descending frequency of PT, and by the All Subjects Combined (Type A + Type B) group for the summary tables with Type A and Type B same dose level combined.

Summaries of AEs will include:

- An overall summary providing subject incidence of the following:
 - Any TEAE
 - Any treatment-emergent serious AE (TESAE)
 - Any treatment-related TEAE
 - Any treatment-related TESAE
 - TEAE by maximum severity
 - Any TEAE leading to study drug discontinuation
 - Any TEAE leading to death

AESIs include injection site-related reactions > Grade 3, lymphopenia > Grade 3 and fever and other injection related (hypersensitivity) reaction > Grade 3, and anaphylaxis.

- TEAEs by SOC and PT
- TEAEs Related to Study Drug by SOC and PT
- TESAEs by SOC and PT
- TESAEs Related to Study Drug by SOC and PT
- TEAEs with Severity Grade ≥ 3 by SOC and PT
- TEAEs by SOC, PT and Maximum Severity Grade
- TEAEs Leading to Study Drug Discontinuation by SOC and PT
- TEAEs of Special Interest by SOC and PT

TEAEs of Special Interest by SOC_PT and Maximum Severity Grade

A by-subject listing of AE data will also be created. Adverse events occurring within 30 days after last dose of study drug and AEs occurring >30 days after the last dose of study drug through the end of the study will be separately summarized. All AEs will be included in the listings. AEs occurring before start of study treatment will be included in the data listings but will not be included in the summary tables of AEs.

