8.3.3.2 Fever and other Injection-Related Reactions

Potential systemic manifestations of infusion/injection-related/hypersensitivity reactions including urticaria, pruritus, and fever have been observed following treatment with EQ001.

For this study, in which the study drug will be administered SC, injection-related reactions are defined as acute onset of an illness (other than those limited to the injection-site, which are described above) occurring within 48 hours of study drug administration that is otherwise unexplained (e.g., by an intercurrent event or the subject's medical history) but does not meet the definition of anaphylaxis Signs of possible injection-related reactions include: fever, chills, pruritus, urticaria, chest pain, dyspnea, hypotension, and hypertension.

In this study, dosing will be done at the study site, and subjects will be monitored for evidence of such reactions. Because individual signs and symptoms of hypersensitivity such as fever are non-specific, investigators are required to clinically evaluate symptoms for etiology to guide management. Guidance for symptomatic and supportive treatment of presumed signs and symptoms of hypersensitivity are included in the protocol (Section 10.7). Subjects experiencing Grade 3 or higher injection-related reactions will be discontinued from study drug treatment. Specific information about such reactions will be collected in the eCRF to fully characterize them.

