8.3.3.3 Anaphylaxis

Anaphylaxis is a severe, potentially fatal, systemic allergic reaction that occurs suddenly after contact with an allergy-causing substance, such as an investigational product. Anaphylaxis will be evaluated using the diagnostic criteria for anaphylaxis as outlined by the 2006 Joint National Institute of Allergy and Infectious Disease/Food Allergy and Anaphylaxis Network Second Symposium on Anaphylaxis (see Appendix D). Subjects with a history of anaphylaxis to foods or drugs will be excluded from the study. Any subject experiencing anaphylaxis considered

Equillium, Inc.	Clinical Study Protocol No. EQ001-19-002	Page 43 of 110

related to the study drug by the investigator will be discontinued permanently from study drug treatment.

Doses will be escalated by cohort only after review of safety data by the DRC, with special attention to hypersensitivity dose-limiting toxicities. Systemic hypersensitivity reactions (Injection-related reactions and anaphylaxis) have also been defined as AESIs, and thus are to be reported with clinical details of the event within 24 hours (Section 12.6) for review by the Sponsor or designee.

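### As printed, SAP 10.3 counts lymphopenia and injection or hypersensitivity reactions as AESIs only above Grade 3, so Grade 3 events drop out of the AESI tables

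*SAP*

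**What the plan says.** SAP 10.3 gives the AESI definition in a single sentence. It opens with "AESIs include injection site-related reactions > Grade 3, lymphopenia > Grade 3" and ends with "fever and other injection related (hypersensitivity) reaction > Grade 3, and anaphylaxis". Three categories therefore carry a strict cut-off at Grade 3, and anaphylaxis carries none.

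The same section plans two AESI tables: "TEAEs of Special Interest by SOC and PT", and a second by SOC, PT and maximum grade. SAP 6.1 adds AESIs to the short list of summaries that pool like doses across Type A and Type B.

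Other statements bear on the cut-off:

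- The list of AE tables in SAP 10.3 includes "TEAEs with Severity Grade ≥ 3 by SOC and PT", with an inclusive operator.
- SAP 10.3 describes the grade in question as "Grade 3 (severe) AE: Significant symptoms requiring hospitalization or invasive intervention", for events that CTCAE does not cover.
- For incomplete records, SAP 10.3 sets missing severity to Grade 3.
- Protocol 8.3.3.3 states: "Systemic hypersensitivity reactions (Injection-related reactions and anaphylaxis) have also been defined as AESIs". No grade floor is visible there.
- Protocol 8.3.3.2 states: "Subjects experiencing Grade 3 or higher injection-related reactions will be discontinued from study drug treatment". Protocol 10.7 repeats that threshold.
- Protocol 13.7 sends the reader to Protocol 12.6 for the AESI definition. That section is not in the public text.

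**The concern.** Protocol 8.3 names lymphopenia and injection-site (hypersensitivity) reactions as the potential adverse drug reactions of EQ001. Protocol 8.4.2 adds that this population is already at increased risk of lymphopenia. The AESI tables are where a reader will look for exactly these risks. If the filter is programmed as printed, a severe (Grade 3) lymphopenia or reaction is not of special interest, and for these three categories the AESI table by maximum grade can only ever show Grades 4 and 5.

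The strict cut-off also fits poorly with its surroundings. It differs from the inclusive operator a few lines away. It leaves a reaction severe enough to end dosing under the protocol outside the AESI count. It also works against the worst-case handling of missing severity.

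**Working it through.** No sample size, event rate or interval is involved. The check applies the printed rule to the SAP's own five-grade scale and sets the passages side by side.

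**Step 1. Grades admitted to the AESI tables.**

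| Category in SAP 10.3 | As printed (above Grade 3) | If inclusive (Grade 3 or above) |
|---|---|---|
| Injection-site reactions | 4, 5 | 3, 4, 5 |
| Lymphopenia | 4, 5 | 3, 4, 5 |
| Fever and other injection-related (hypersensitivity) reactions | 4, 5 | 3, 4, 5 |
| Anaphylaxis | any | any |

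The operator decides the fate of one grade, Grade 3, in three of four categories.

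**Step 2. Missing severity.** An event with no recorded grade becomes Grade 3. Under the printed rule, 3 > 3 is false and the event leaves the AESI tables. Under the inclusive rule, 3 ≥ 3 is true and it stays. An imputation meant to be conservative acts in the opposite direction in these tables.

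**Step 3. Systemic reactions against the protocol.** The SAP's third category has nearly the same name as Protocol 8.3.3.2, and Protocol 8.3.3.3 calls injection-related reactions AESIs without a visible grade limit. Read that way, Grades 1 to 5 qualify. The printed SAP rule then omits Grades 1, 2 and 3; an inclusive rule would still omit Grades 1 and 2. This discrepancy does not depend on the operator.

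**Step 4. Where Grade 3 events remain visible.**

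| Output | Carries these Grade 3 events? |
|---|---|
| Two AESI tables (SAP 10.3) | No, as printed |
| Pooled Type A + Type B AESI summary (SAP 6.1) | No, as printed |
| TEAEs of Grade 3 or above, by SOC and PT | Yes |
| TEAEs by SOC, PT and maximum grade | Yes |
| TEAEs leading to discontinuation | Yes, if the event led to discontinuation |
| Graded laboratory abnormalities, worst grade and shift tables (SAP 10.4) | Yes, for lymphocyte counts |
| By-subject listings | Yes |

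**Step 5. The pooled view.** SAP 6.1 names four pooled same-dose summaries: AEs by SOC and PT, AESIs, SAEs, and AEs leading to discontinuation. The Grade 3 or above table is not among them. A non-serious Grade 3 lymphopenia without discontinuation would appear in the pooled 1.6 mg/kg summaries only as an ungraded preferred term. By the planned numbers, that pool is 6 Type A subjects plus up to about 20 Type B subjects, or up to about 26.

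**The case against.** **The operator may be a reading artefact.** An underlined greater-than sign and a true greater-or-equal character are extracted from a PDF in different ways, so one can lose its bar while the other survives. Operators are also mixed elsewhere in these documents. The neutrophil criterion is inclusive in Protocol 9.1.1 and strict in 9.1.2, and the SLEDAI-2K split differs between the protocol synopsis and Protocol 13.9.2. This stands. A bare greater-than sign is weak evidence of intent, and the source file must be checked first. It does not remove the discrepancy for systemic reactions in Step 3 of the working.

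**The governing section is not visible.** Protocol 12.6 holds the AESI definition. The absence of a grade limit in 8.3.3.3 is silence in a partly redacted document. A reader might infer that the SAP contradicts the protocol's full AESI definition; the documents do not show that. They show only a mismatch with 8.3.3.3 as far as it can be read.

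**Grade 3 or higher is not a general protocol threshold.** The visible text uses it for injection-related reactions, as a discontinuation rule. No visible protocol passage sets an AESI grade for lymphopenia or injection-site reactions. This stands, and it is why an inclusive cut-off for those two categories has to be made subject to 12.6.

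**Nothing is lost from primary safety reporting.** The primary endpoint comprises TEAEs, TESAEs, laboratory values, vital signs, ECG and physical examinations; AESIs are not a named component. A reader might infer that Grade 3 lymphopenia or reactions would vanish from the report, or that reactions ending treatment would be hidden. Neither follows, because other planned outputs carry them. What remains is that the tables dedicated to these risks, and the pooled version of them, would understate them.

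**Conclusion.** The point holds for the SAP as printed, and it is limited to the AESI outputs. Grade 3 events in three of the four categories, including those imputed to Grade 3, drop out of both AESI tables and the pooled AESI summary. Anaphylaxis is unaffected. It would be too strong to say that all AESIs are confined to events above Grade 3, that the events go unreported, or that a strict cut-off was certainly intended.

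The size is one severity grade in three categories. It cannot be turned into a number of subjects, because the visible text gives no expected rate of Grade 3 lymphopenia or reactions. Nor is a confidence interval for an AESI proportion a stated output: SAP 6.1 mentions intervals only for selected clinical activity parameters.

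The conclusion about Grade 3 assumes that the operator in the source SAP is the one printed. The conclusion about Grade 1–2 systemic reactions does not depend on the operator, but assumes that Protocol 12.6 adds no grade floor to what 8.3.3.3 says. The correction is worth making because safety is the primary objective and these are the drug's identified risks.

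**What to change.** 1. Check the operator in the source SAP. If it is already inclusive, the Grade 3 part of this point falls away.
2. If it is strict, change the AESI definition for injection-site reactions and lymphopenia to Grade 3 or above, subject to agreement with Protocol 12.6.
3. Define systemic injection-related (hypersensitivity) reactions and anaphylaxis for the AESI tables as Protocol 8.3.3.3 and 12.6 define them. If 12.6 has no grade floor, remove the one in the SAP.
4. SAP 2.2 reports that a Type A analysis has already been run on frozen data. Confirm which AESI filter it used, and make it match the final analysis so that the pooled summary is consistent.

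The cost is a sentence in the SAP and a filter in the two AESI tables and their pooled version. No new data are needed. AESI counts may become less favourable.

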Equillium, Inc. Clinical Study Protocol No. EQ001-19-002 Page 12 of 110

The MTD determination will be made based only on Type A Cohorts. Dose escalation is allowed to proceed if no predefined stopping criteria are met and the DRC recommends that it is safe to proceed.

Type B

Up to approximately 20 subjects will be enrolled and dosed in the Type B Cohort. Subjects will receive a total of 13 doses of EQ001 1.6 mg/kg administered SC every 2 weeks over 24 weeks. All subjects must be on a stable dose of mycophenolate mofetil (MMF) or mycophenolic acid (MPA) for the duration of the study. Subjects that require induction treatment with pulse steroid treatment of methylprednisolone ≥500 mg or equivalent will undergo a rapid steroid taper with a 20% reduction per week. The targeted goal is to reach a prednisone dose of 10 mg or less per day by Week 10.

The study will be conducted in 3 defined periods, described below:

- 1. Screening Period
 - a. **Type A Cohorts:** The Screening Period for Cohort A subjects will be up to 4 weeks in duration, starting with the first screening procedure in the Schedule of Events (SOE; excluding the informed consent), and completed prior to Study Day 1 (Section 5.2)
 - b. **Type B Cohort:** The Screening Period for Cohort B subjects will be up to 6 weeks in duration (excluding the informed consent) and completed prior to Study Day 1 and may be completed over the course of multiple clinic visits. (Section 5.3).
- 2. Treatment Period
 - a. **Type A Cohorts**: The Treatment Period for Cohort A subjects will be 4 weeks in duration, beginning on Day 1 with the first study drug dose. During the Treatment Period, 2 doses of study drug will be

[figure not shown]
- administered subcutaneously (SC), 1 dose each on Days 1 and 15. Subjects will return to the study site for follow-up evaluations according to the SOE (Section 5.2).
- b. **Type B Cohort**: The Treatment Period for Cohort B subjects will be 24 weeks in duration, beginning on Day 1 with the first study drug dose. During the Treatment Period, 13 doses of study drug will be administered SC, 1 dose each on Days 1, 15, 29, 43, 57, 71, 85, 99, 113, 127, 141, 155, and 169. Subjects will return to the study site for follow-up evaluations according to the SOE (Section 5.3 and Section 5.4).
- 3. Follow-up Period
 - a. **Type A Cohorts**: The Follow-up Period for Cohort A subjects will end approximately 6 weeks after the last dose of study drug (Section 5.2)

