 - b. **Type B Cohort**: The Follow-up Period for Cohort B subjects will end approximately 12 weeks after the last dose of study drug (Section 5.4)

Note: Contraception requirements must be continued for 130 days after the last dose of study drug for Type A and B Cohorts.

Written informed consent for study participation may be obtained up to 4 weeks prior to the Screening Visit for Type A Cohort subjects and 8 weeks prior to the Screening Visit for Type B Cohort subjects. Evaluation of eligibility will be based on laboratory results, medical history, concomitant and prior medications, vital signs, 12-lead ECG, physical examination, pregnancy testing (if applicable), and, in Type B Cohort, renal biopsy results.

Subjects will be evaluated for eligibility to receive the next dose based on laboratory and clinical criteria prior to each dose. The pre-dose laboratory evaluations may be performed at a local or central laboratory up to 14- days prior to the next target dosing day or on the target dosing day. If a subject discontinues study drug treatment prior to the last dose, they will be asked to return to the clinical study site to complete all follow up visits, as described in the SOE.

If a subject withdraws from the study, they should complete an Early Termination Visit.

added based on emerging data to meet the objectives of the study.

Inclusion Criteria:

Type A Cohort Inclusion Criteria. Subjects will be required to meet all of the following inclusion criteria in order to be eligible for study enrollment:

1. Is male or female, age \geq 18 and \leq 75 years

3. Has previously been documented to have met or currently meets Systemic Lupus International Collaborating Clinics (SLICC) and/or American College of Rheumatology (ACR) criteria for SLE

[figure not shown]
4. Received at least 1 immunosuppressive or immunomodulatory treatment (including antimalarials) for SLE at any time in the past or currently

6. Has documented elevation of antinuclear antibodies (ANA) in the past or during Screening

[figure not shown]
7. Restricted SLE treatments (e.g., other immunosuppressive medications, glucocorticoids, and antimalarials) are stable and/or washed out at Screening

[figure not shown]
8. Changes in SLE drug treatment(s), including increased doses of glucocorticoids or other SLE treatments, are not anticipated during the study

9. During Screening, has adequate hematologic function

Page 15 of 110

[figure not shown]

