5.1 Safety Population

The Safety Population consists of all subjects who receive any study drug. All safety data summaries will use this population.

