9.3 Anti-drug antibody (ADA)

Serum from available timepoints will be analyzed for detection of anti-drug antibodies (ADA) against EQ001. A NAB assay will be performed on the same samples, if required. ADA sampling may be requested by the

Sponsor at an unscheduled visit to further evaluate safety in individual subjects. ADA and neutralizing ADA results will be presented in a by-subject listing for the Safety Population with Type A and Type B combined.

10 Safety

All safety analyses will be performed using the Safety Population.

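### SAP 10.3 splits AEs at 30 days after the last dose, but the two periods appear very unequal in length, so crude percentages cannot show whether risk changes off drug

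*SAP*

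**What the plan says.** SAP 10.3 calls for separate summaries of "Adverse events occurring within 30 days after last dose of study drug and AEs occurring >30 days after the last dose of study drug", the second group running to the end of the study. It does not say when the first period begins, and it gives no denominator for either summary.

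The general rules supply the likely format. AE analyses are "TEAEs summarized descriptively by number of subjects with an event (n), and percentage", by system organ class, preferred term and grade, with each subject counted at most once per term (SAP 10.3). On the denominator, SAP 5.1 says "The Safety Population consists of all subjects who receive any study drug" and adds "All safety data summaries will use this population". The opening of SAP Section 10 repeats this: "All safety analyses will be performed using the Safety Population".

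Follow-up duration is summarized under disposition (SAP 7.1) and exposure duration under SAP 10.1. The readable text does not use either as a denominator for AEs.

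The schedule fixes the period lengths. Type B subjects receive "1 dose each on Days 1, 15, 29, 43, 57, 71, 85, 99, 113, 127, 141, 155, and 169", and "The Follow-up Period for Cohort B subjects will end approximately 12 weeks after the last dose of study drug" (Protocol 5.1). Type A subjects are dosed on Days 1 and 15 and followed for about 6 weeks after the last dose.

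**The concern.** A percentage of subjects with an event grows with the time over which events are counted. If one period is several times longer than the other, the shorter one shows fewer affected subjects even when nothing about the risk has changed. Tables split at 30 days after the last dose invite a reader to ask whether events settle or emerge once EQ001 has been stopped.

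Safety is the primary objective and there is no concurrent control. In the readable text this split is the only AE summary that separates late off-drug events from the rest. At stake is whether a lower late percentage is taken as evidence that risk falls after treatment.

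**Working it through.** **Inputs.** Dosing days and follow-up lengths are from Protocol 5.1, total time on study from Protocol 8.2, and last-visit days from SAP 10.7. The documents give no AE or dropout rates, so every percentage below is an assumption used for illustration.

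**1. Reproduce the schedule.**
- Type B: last dose 1 + 14 × 12 = Day 169. End 169 + 84 = Day 253. (253 − 1)/7 = 36 weeks, matching the 36 weeks in Protocol 8.2 and FU4 at Day 253 in SAP 10.7.
- Type A: last dose 1 + 14 = Day 15. End 15 + 42 = Day 57. (57 − 1)/7 = 8 weeks, matching the 8 weeks in Protocol 8.2 and FU2 at Day 57.

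**2. Period lengths for a subject given all doses**, taking the early period as first dose to last dose + 30 days.
- Type B: early 169 + 30 = 199 days, late 253 − 199 = 54 days, ratio 54/199 = 0.271.
- Type A: early 15 + 30 = 45 days, late 57 − 45 = 12 days, ratio 12/45 = 0.267.

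**3. Expected late percentage under a constant hazard**, everyone entering the late period: late = 1 − (1 − early)^ratio.

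| Early | Late, Type B | Late, Type A |
|---|---|---|
| 20% | 5.9% | 5.8% |
| 50% | 17.1% | 16.9% |
| 80% | 35.4% | 34.9% |

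**4. How large a real rise would be hidden.** The percentages become equal only when the late hazard is 199/54 = 3.7 times the early one in Type B (45/12 = 3.75 in Type A). A doubled late hazard in Type B, with 20% early, gives 1 − 0.8^(2 × 54/199) = 11.4% late, which still looks like a fall.

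**5. Type B subjects who stop early**, if followed for 12 weeks after their own last dose. The late period stays at 54 days and the early one is the last dose day + 30.

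| Last dose received | Day | Early days | Late/early |
|---|---|---|---|
| 6th | 71 | 101 | 0.53 |
| 3rd | 29 | 59 | 0.92 |
| 2nd | 15 | 45 | 1.20 |
| 1st | 1 | 31 | 1.74 |

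**6. The other reading of the early period.** If it were only the 30 days after the last dose, the ratio would be 54/30 = 1.8 in Type B and 12/30 = 0.4 in Type A. On-treatment AEs would then fall in neither summary, so this reading is less natural, but the text does not exclude it.

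**7. What each remedy achieves.** Assume 20 Type B subjects and a constant hazard giving 60% over 199 days. Four stop after dose 6, and two of those four have no late follow-up.
- All treated as denominator: 55.4% early, 19.8% late.
- Only subjects who enter the late period as denominator: 22.0% late.
- Person-time: 16 × 199 + 4 × 101 = 3,588 days early and 18 × 54 = 972 days late. The underlying first-event rate is −ln(0.4)/199 = 0.46 per 100 patient-days, or 1.68 per patient-year, in both periods.

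Changing the denominator recovers little. The rate removes the artefact.

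**8. Late person-time if all complete.** Type B: 20 × 54/365.25 = 3.0 patient-years. All Type A: 30 × 12/365.25 = 1.0. One Type A cohort: 6 × 12/365.25 = 0.2, where a single event reads about 5 per patient-year.

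**The case against.** The strongest reply is that the problem depends on things the SAP does not say. The start of the early period is inferred, and on the alternative reading the imbalance in Type B reverses. A reader might infer that a fall after treatment is guaranteed by construction; the text does not establish that. A reader might also infer that subjects who leave within 30 days of the last dose are counted as event-free in the late table. The SAP names an analysis population but does not state the denominator of the split tables. Subjects who only stop drug are asked to complete follow-up, so they can still enter the late period. SAP 6.2 (key definitions) is not visible, so one can say only that no person-time or at-risk count appears in the readable text. All of this stands, and it limits the claim.

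A second reply is that a late signal would not be lost. Every AE is listed by subject, in a trial of about 50. UPCR, SLEDAI-2K, eGFR and laboratory values are summarized by visit, and renal response is reported again at FU4. Protocol 8.8.1 has the Data Review Committee continue periodic safety review. This also stands: the documents do not support the inference that late events or rebound disease would go unseen.

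Third, no formal comparison of the periods is planned (SAP 6.1), and a constant hazard does not suit every event. Injection-related reactions are defined by onset within 48 hours of dosing (Protocol 8.3.3.2), so a fall after stopping is expected for them. That is right, but it does not help the crude table, which cannot separate a real fall from a shorter window.

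**Conclusion.** The point holds with limits. Followed as its general rules imply, and with the early period starting at first dose, SAP 10.3 would place side by side two percentages whose counting periods differ about 3.7-fold for subjects given all doses. With unchanged risk, the late figure would be about 0.3 to 0.45 of the early one for early percentages between 20% and 80%. The two cannot be read as a change in risk off drug.

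This rests on the inferred period start, on Safety Population denominators, on most subjects receiving all doses, and on a constant hazard for the illustrated sizes. In Type B the distortion shrinks with early stopping and changes direction only for subjects who stop after one or two doses. The weakness lies in how the tables would be interpreted. Person-time rates would make a clear and inexpensive improvement.

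**What to change.** In SAP 10.3:

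1. State that the early period starts at first dose and ends 30 days after the last dose, and that the late period runs from the next day to the end of follow-up.
2. For each period, show the number of subjects with any follow-up in it and the total person-time.
3. Beside the percentages, add events per patient-year, or subjects with a first event in that period per patient-year, for overall TEAEs, TESAEs, infections and AESIs. This is the essential part. Restricting the late denominator to subjects who enter that period is a useful secondary step.
4. Present the rates for Type B and for all Type A doses combined, not for single six-subject cohorts.

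The cost is a few derived columns in tables already planned. The first-dose, last-dose and last-contact dates are already used in SAP 7.1 and 10.1, so no new data are needed. Type A has already been analysed once, but SAP 2.2 plans a final analysis of all data after Type B lock, and the change can be made there. The drawback is imprecision: late person-time is at most about 3 patient-years in Type B and 1 in Type A at the planned numbers, so late rates will have wide intervals.
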